#### **applicable** receive any treatment with IMP.

## 11.3.1.9 Assessment of outcome

The Investigator must assess the outcome of an AE using the definitions below and record it on the AE Log of the eCRF:

Recovered/resolved	The subject has recovered completely, and no symptoms remain.
Recovering/resolving	The subject's condition is improving, but symptoms still remain.
Recovered/resolved with sequelae	The subject has recovered, but some symptoms remain (for example, the subject had a stroke and is functioning normally but has some motor impairment).
Not recovered/not resolved	The subject's condition has not improved, and the symptoms are unchanged (for example, an atrial fibrillation has become chronic).
Fatal	
Unknown	

# 11.3.1.10 Reporting of action taken with trial treatment

The Investigator must report the action taken with trial treatment using the definitions below and record it on the AE Log of the eCRF:

Dose increased	Not applicable for the present trial
Dose not changed	
Dose rate reduced	Not applicable for the present trial
Dose reduced	Not applicable for the present trial
Drug interrupted	Not applicable for the present trial
Drug withdrawn	
Not applicable	
Unknown	Not applicable for the present trial

# 11.3.1.11 Collecting adverse events

AEs identified using any of the following methods will be recorded:

- AEs spontaneously reported by the subject
- AEs observed by the Investigator or medical personnel
- AEs elicited based on non-leading questions from the Investigator or medical personnel

# 11.3.1.12 Recording adverse events

AEs must be recorded in the AE Log of the eCRF. The Investigator must provide information on the AE, preferably with a diagnosis or at least with signs and symptoms; start and stop dates, start and stop time; intensity; causal relationship to IMP; action taken, and outcome.

If the AE is serious, this must be indicated in the eCRF.

AEs, including out-of-range clinically significant clinical safety laboratory values, must be recorded individually, except when considered manifestations of the same medical condition or disease state; in such cases, they must be recorded under a single diagnosis.

# 11.3.1.13 Reporting of serious adverse events

SAE reporting should be performed by the Investigator within 24 hours of awareness via the eCRF. All available information regarding the SAE should be entered in the eCRF SAE form (*i.e.*, term, intensity, causality, outcome, SAE criteria, action taken, narrative including rational for causality assessment). for the specific subject. By saving the event as "serious" in the eCRF and once the Investigator has signed-off of the event, an e-mail alert is automatically sent to predefined recipients to highlight that an SAE has been registered. The same information is automatically sent to: [contact].

The SAE report is reviewed by a designated person at CTC's Pharmacovigilance (CTC PV) department to ensure that the report is valid and correct. For fatal or life-threatening SAEs where important or relevant information is missing, immediate follow-up is undertaken and queries to the site are raised. Investigators or other site personnel should inform CTC PV of any follow-up information (including rational for changes, *e.g.*, changes in causality assessment and intensity, that should be described in the SAE narrative) on a previously reported SAE immediately but no later than within 24 hours of awareness.

If the SAE report in the eCRF is updated and signed by the Investigator, a new e-mail alert will be sent.

If any additional documentation is required (*e.g.*, autopsy report), CTC PV will request this information from the trial site.

In case the eCRF cannot be accessed, the SAE should be reported by manual completion of the paper SAE Form, provided in the Investigator Site File (ISF). The completed, signed and dated paper SAE Form should, within 24 hours, be scanned and delivered via encrypted e-mail secure file transfer to CTC's SAE inbox at [contact].

A copy of the paper SAE form must also be e-mailed to CTC at: [contact].

The trial site should notify the site Monitor via phone or e-mail about the submission of the SAE report. As soon as the site personnel have access to the eCRF, the SAE should be reported electronically as well.

The Sponsor has delegated to CTC the responsibility to report SAEs to the competent authority (CA) and IEC in accordance with local regulations.

## 11.3.1.14 Reporting of SUSARs to EudraVigilance, local CA and IEC

The term SAR is used whenever either the Investigator or Medical Monitor deems a blinded SAE as related to IMP. If a SAR is assessed as unexpected based on the reference safety information (RSI)/IB, it is a potential SUSAR and under such circumstances an EudraVigilance reporter will be unblinded. In case the event is regarded as a SUSAR the EudraVigilance reporter will report the SUSAR to the CA, via the EudraVigilance database, and to the IEC in accordance with local regulations and CTC SOPs within the following timelines:

- 7 calendar days if fatal or life-threatening
- 15 calendar days if non-fatal and non-life-threatening

The clock for expedited initial reporting (Day 0 = Di 0) starts as soon as the information containing the minimum reporting criteria has been received by the Sponsor. The date should be documented on an acknowledgement receipt.

The Medical Monitor is responsible for medical review of the SAE narrative in the Council for International Organisations of Medical Sciences (CIOMS) form (or equivalent) prior to expedited reporting. The CIOMS form will be reviewed and approved by the Sponsor's Medical Representative, including expectedness and causality assessment.

The Sponsor has delegated to CTC the responsibility to inform the Investigators concerned of relevant information about SUSARs that could adversely affect the safety of subjects.

The Sponsor or delegate is responsible for, once a year throughout the clinical trial (or on request), submitting a safety report to the CA and the IEC taking into account all new available safety information received during the reporting period.

## 11.3.1.15 Treatment and follow-up of adverse events

Subjects with AEs that occur during the trial must be treated according to daily clinical practice at the discretion of the Investigator.

AEs must be followed up until they have reached a "final outcome" (recovered/resolved, recovered/resolved with sequelae, recovering/resolving, not recovered/not resolved/ongoing, fatal, or unknown) or the subjects' participation in the trial ends, whichever comes first. At the end-of-trial visit, information on new AEs, if any, and stop dates for previously reported AEs must be recorded (if known). AEs assessed as stable by the Investigator at the end-of-trial visit will not have to be followed up until resolution.

It is the responsibility of the Investigator to follow up on all SAEs until the subject has reached a "final outcome" or the subjects' participation in the trial ends, whichever comes first.

SAEs and severe, non-serious AEs assessed as "Related" to IMP, still ongoing after the trial participation has ended, should be followed on a regular basis according to the Investigator's

clinical judgment until a "final outcome" has been established and to report to the Sponsor all relevant new information using the same procedures and timelines as those for the initial report. Relevant information includes discharge summaries, autopsy reports, and medical consultation.

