# 6.1.7 *Clinical experience*

This is a first-in-human (FIH) trial, C106 has not yet been studied in humans.

The safety of activating the AT2R has previously been evaluated with the AT2R agonist C21 in 3 completed Phase 1 trials (C21-001-16, C21-002-16, and C21-003), in 1 completed Phase 2 trial in hospitalised patients with COVID-19 (VP-C21-006) and in 1 completed Phase 2 trial in patients with Raynaud's phenomenon secondary to SSc (VP-C21-004) with a total of 146 subjects exposed to at least one oral dose of C21 in these trials. Across the trials, C21 was generally well tolerated at daily doses up to 200 mg, whereas doses of 200 mg twice daily (in total 400 mg daily) for 8 days resulted in reversible hair loss in 6 out of 6 subjects occurring within 2 weeks after end of dosing and improving within 8 weeks (C21-003). In addition, there is one ongoing IPF phase 2 trial with C21 (VP-C21-005). After administration of 100 mg C21 twice daily, mild to moderate "hair fall or hair loss" has been reported in 5 subjects in this trial, where 4 out of the 5 cases have resolved and 3 out of 5 subjects continued treatment with C21. The observed hair loss was considered related to C21 treatment and due to a pharmacological effect of stimulation of the AT2R. This adverse reaction was not observed at lower dose levels in any of the completed trials. For additional information, see Section 6.3.

Across the Phase 1 trials, the most commonly observed treatment-emergent adverse event (AE) considered related to treatment was headache. C21 is currently in Phase 2 clinical development for treatment of IPF and in Phase 3 clinical development for treatment of moderate to severe COVID-19.

[figure not shown]
In the present trial, 24 subjects have been dosed with C106 in 4 single dose cohorts (5, 30, 60 and 180 mg). In each cohort, 8 subjects have been administered C106 or placebo in a 3:1 ratio. The interim PK analysis showed that C106 had a fast absorption with a  $T_{max}$  at 20-40 minutes and a mean terminal half-life ( $T_{1/2}$ ) of approximately 11 hours. The plasma exposure of C106 was lower than expected at all dose cohorts evaluated, and the dose proportionality was non-linear. Interim PK analysis of plasma exposure in terms of Cmax and AUCinf is presented in Table 8.3-2 in Section 8.3.1.

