A Phase 1 clinical trial with C21 reported reversible hair loss in 6 healthy subjects exposed to 200 mg C21 twice daily for 8 days (400 mg per day) (C21-003). The events included hair loss on the head and the body and occurred on average 11 (ranging from 8 to 14) days after end of dosing. Regrowth of the hair was observed in all subjects within 8 weeks after end of dosing. The observed hair loss was considered related to treatment with C21 and was possibly due to a pharmacological effect of stimulation of the AT2R. No cases of hair loss have been reported at dose levels up to 100 mg C21 twice daily for 7 days or after single doses of 200 mg in any of the completed, randomised, controlled clinical trials with C21.

As described in the current version of the IB (cut-off date 15-Mar-2022), mild to moderate "hair fall or hair loss" has been reported in 5 subjects in the ongoing, open-label IPF phase 2 trial after administration of 100 mg C21 twice daily (VP-C21-005). 4 out of the 5 cases have resolved; 3 out of 5 subjects continued treatment with C21. The characteristics and nature of the 'hair fall or hair loss' reported in this trial appear to be different from the hair loss reported in the phase 1 trial, and the relationship to treatment is unclear.

Although the mechanism for the reversible hair loss is not known, it cannot be excluded that it is a potential class effect related to high dose AT2R stimulation. It is therefore a risk that the subjects who participate in Part B of the current trial may experience hair loss. Hair loss of moderate intensity (*i.e.*, Common Terminology Criteria for Adverse Events [CTCAE] grade 2) in 2 subjects assessed as related to the IMP administration has hence been included as a stopping criterion for dose escalation, see Section 8.3.5.

The phototoxicity of C106 has not been investigated but based on the molar extinction coefficient (MEC) value obtained from absorbance studies a phototoxic potential cannot be excluded. Thus, sun protection, as defined in Section 9.6.1, should be used during the study.

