# 8.1.2 Multiple Ascending Dose (MAD) part of the trial

In Part B, repeated, oral doses of C106 will be administered in 4 sequential dose cohorts. Within each cohort, subjects will be randomised to receive C106 (n=6) or placebo (n=2). The initial dose, dose escalations, and dosing schedule will be based on emerging safety, tolerability, and PK data observed in the SAD part of the trial (Part A) and on emerging data from the MAD part. Each dose level during the Part B will be selected such that the predicted maximum exposure will not exceed the maximum exposure (based on AUC and  $C_{max}$ ) in previously evaluated SAD cohorts. The proposed doses are 40, 100, 180 and 240 mg BID. Twice daily dosing for 8 days is planned. Based on emerging PK data, once daily (QD) dosing may be applied if recommended by the iSRC. The number of dosing days may also be changed based on PK data from Part A (SAD), with the aim to reach steady state during the dosing period. The treatment duration will, however, not exceed the treatment duration in preclinical toxicology studies *i.e.*, 28 days. One additional dose cohort can be explored based on emerging safety, tolerability, and PK of the drug, if recommended by the iSRC. The maximum oral daily dose in Part B will not exceed 480 mg C106.

Subjects will come for 3 visits to the CRU. Screening (Visit 1) will take place within 4 weeks of the first dose (Day -28 to Day -1) and will include the subject's signing of the informed consent and an eligibility check, see Table 8.1-3 for details. At Visit 2, subjects will reside at the CRU from Day -1 (the day before IMP administration) until Day 10 for 8 days multiple dose IMP administration, safety, tolerability and PK assessments, see Table 8.1-3, Table 8.1-4 (Day -1 to Day ) and Table 8.1-5 (Day 8 to Day 10). Subjects must fast from 2 hours prior to each IMP administration until 1 hour after. During fasting, water, but no other drinks, is allowed as desired. No drinks are allowed for 1 hour before and 1 hour after dosing. On Day 8, only the morning dose will be administered (*i.e.*, in total 15 doses are planned).

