If 2 subjects on active treatment in the same cohort have a grade 2 hair loss (≥50% normal for that individual that is readily apparent to others; a wig or hair piece is necessary if the patient desires to completely camouflage the hair loss; associated with psychosocial impact) assessed as related to the IMP administration.	
 
Stop dosing of subjects with hair loss. Await dosing of additional subjects until the iSRC's recommendation and the Sponsor's decision on continuation.
 
Unblinding of the subjects with potential adverse reactions. Only voting members of the iSRC will be unblinded.
 
Evaluation by iSRC. The iSRC makes recommendation to Sponsor.
 
Sponsor decides how to proceed.
 
Both subjects received active treatment, i.e., met stopping criterion: stop further dosing at this dose level for all subjects. Sponsor decides if the trial will be terminated or if dosing will resume at a lower dose level.
 

If the next planned dose level is predicted to result in an exposure exceeding either an AUC 0-24 of 15 900 ng*h/mL or a $C_{max}$ of 8730 ng/mL based on the NOAEL in the most sensitive non-rodent species (female dog). 	
 
Evaluation by iSRC. The iSRC makes recommendation to Sponsor.
 
Sponsor decides if the trial will be terminated or if dosing in the next cohort should commence at a lower dose level than intended.
 

Final dosing stop and termination of	trial
If 2 subjects on active treatment in different cohorts have SAEs assessed as related to IMP administration	
 
Stop dosing of subjects with potential SAR. Withdrawal of subjects.
 
Unblinding of subjects with potential SARs. Only voting members of the iSRC will be unblinded.
 
Evaluation by iSRC. The iSRC makes recommendation to Sponsor.
 

	4. Subjects meet stop criterion: Termination of trial. ation to this criterion, the maximum exposure observed in individual subjects

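### Related moderate hair loss, a Part B stopping event, is outside the AE follow-up that continues after participation, so it could be closed unresolved about two weeks after the last dose

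*Combined protocol and SAP*

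**What the plan says.** Section 6.3 of the protocol describes hair loss in all 6 healthy subjects given the analogue C21 at 200 mg twice daily for 8 days. It says of the mechanism that "it cannot be excluded that it is a potential class effect related to high dose" stimulation of the receptor, and it names hair loss as a risk for Part B subjects. The C21 events "occurred on average 11 (ranging from 8 to 14) days after end of dosing". On recovery, Section 6.3 says "Regrowth of the hair was observed in all subjects within 8 weeks after end of dosing", while Section 6.1.7 describes the same events as "occurring within 2 weeks after end of dosing and improving within 8 weeks".

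The protocol responds with a Part B stopping criterion in Table 8.3-4: "If 2 subjects on active treatment in the same cohort have a grade 2 hair loss", assessed as related. Section 6.3 calls this grade moderate, as does the intensity scale in Section 11.3.1.7.

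For Part B dosing, Section 8.1.2 says "On Day 8, only the morning dose will be administered". The end-of-trial visit (Visit 3) is on Day 22 ± 2. AE collection stops at that visit (Section 11.3.1.6).

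Section 11.3.1.15 follows an AE until a final outcome or the end of participation, whichever is earlier. Its list of final outcomes includes recovering and not recovered or ongoing. It adds that "AEs assessed as stable by the Investigator at the end-of-trial visit will not have to be followed up until resolution". Only SAEs, and AEs that are severe but not serious and judged related, if "still ongoing after the trial participation has ended, should be followed on a regular basis".

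**The concern.** The follow-up rule and the stopping rule use different thresholds. An event that can halt escalation in Part B is moderate, whereas continued follow-up of a non-serious event starts at severe. Related grade 2 hair loss that is still present at Visit 3 therefore has no rule that carries it forward. If C106 behaved like C21, the event would start shortly before Visit 3 and improve well after it.

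Safety and tolerability are the primary objective. Evidence that this effect reverses comes from C21, not C106. What is at stake is whether this trial can say anything about resolution if the event occurs.

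**Working it through.** **Inputs.** Screening up to 28 days, Visit 3 on Day 22 ± 2, and stated Part B participation of up to 47 days (Section 8.1.2). Last dose on Day 8 (Section 8.1.2). C21 onset 8 to 14 days after end of dosing, mean 11, and regrowth within 8 weeks = 56 days (Section 6.3).

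**1. The plan's own duration figures.** Participation = screening + visit day + window.
- Part A: 28 + 7 + 2 = 37, which matches the stated 37.
- Part B: 28 + 22 + 2 = 52, against the stated 47. Without the window the sum is 28 + 22 = 50, and at the earliest visit 28 + 20 = 48. No variant gives 47. A total of 47 would put the last day at 47 − 28 = Day 19, for example a visit on Day 17 ± 2, only 7 to 11 days after the last dose.

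This is a separate inconsistency. The steps below use Day 22 ± 2, which gives the longer follow-up.

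**2. C21 timing on this trial's calendar.** Onset: Day 8 + 8 = Day 16 to Day 8 + 14 = Day 22, mean Day 8 + 11 = Day 19. Regrowth horizon: Day 8 + 56 = Day 64.

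**3. Follow-up, shortfall and observation time.** Follow-up = visit day − 8. Shortfall = 56 − follow-up. Observation = follow-up − onset.

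| Visit 3 | Days after last dose | Days short of 56 | Days observed, onset at 8 / 11 / 14 days |
|---|---|---|---|
| Day 20 | 12 | 44 | 4 / 1 / −2 |
| Day 22 | 14 | 42 | 6 / 3 / 0 |
| Day 24 | 16 | 40 | 8 / 5 / 2 |

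The −2 means that onset would fall two days after AE collection had ended for that subject.

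**4. The rules side by side.** Table 8.3-4 acts on grade 2. Section 11.3.1.7 labels grade 2 moderate and grade 3 severe. Section 11.3.1.15 continues non-serious related events only if severe. A grade 2, non-serious, related event therefore meets the stopping grade but not the continued-follow-up grade.

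**5. Other provisions that might cover it.**
- Sections 6.3 and 8.3.6 have the iSRC consider hair loss that emerges after the 48-hour cut-off. That serves the escalation decision and does not ask for the outcome.
- Sections 8.1.2 and 8.3.6 allow one added visit for safety and PK. It is optional and not tied to resolution.
- Section 11.3.1.6 requires later reporting only of SAEs that the Investigator learns of.
- Section 11.3.1.16 follows pregnancy outcomes after participation ends, so the protocol already has one event-specific extension. Hair loss has none.

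**The case against.** The strongest reply is that the text permits more than it requires. The sentence on stable AEs only relieves the Investigator of a duty, and it does not obviously release hair loss that is new and still changing. It can even be read to imply that unstable AEs are followed further. The Investigator may continue voluntarily, the iSRC may add a visit, and the iSRC charter, which is a separate document, may say more. An Investigator could also classify a case as an important medical event under Section 11.3.1.2, which would bring it into the SAE rule. No objective or endpoint concerns reversibility, and the nominal visit reaches the upper end of the C21 onset range.

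The C21 experience may also not transfer. A single 200 mg dose of C21 gave a mean AUCinf of 5619 ng*h/mL (Section 8.3.1). C106 at 180 mg gave 2244 (Table 8.3-2), a ratio of 2244 / 5619 = 0.40. C106 PK is non-linear, so exposure at 240 mg twice daily cannot be read from this. The 6-of-6 figure is an upper scenario, not a forecast.

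Much of this stands, and it limits the wording to could be closed. It does not remove the gap. For evolving hair loss the operative text is the earlier-of rule, and that rule ends follow-up with participation. Each of the other routes is discretionary, and none requires a resolution outcome.

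**Conclusion.** The point holds as a cheap improvement to outcome collection in Part B. Related grade 2 hair loss ongoing at Visit 3 is outside the continued-follow-up rule and could be closed unresolved 12 to 16 days after the last dose. With C21-like timing it would have been observed for 0 to 6 days at the nominal visit. The shortfall of 40 to 44 days is a maximum: the 8 weeks runs from the end of dosing, comes from another compound, and bounds regrowth or improvement, not documented full recovery.

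A reader might infer more than the documents support:
- That no outcome would be recorded. Section 11.3.1.9 requires one for every AE, so recovering or not recovered would be entered. What may be missing is whether and when the event resolved.
- That the sponsor accepts hair loss because it is reversible. Section 6.3 does not argue this. It says the mechanism is unknown and gives the stopping criterion as the response.
- That subjects would leave at the height of the event. The documents say nothing about a peak. They support only that Visit 3 would come soon after onset.

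**What to change.** Reconcile Sections 6.3, 8.3.5 (Table 8.3-4) and 11.3.1.15 so that outcome collection after participation also covers related hair loss that meets the Table 8.3-4 grade and is still ongoing at Visit 3. Remote contact would be enough. State what counts as resolved, and report the outcome and, where known, the time to resolution with the AE tables of Section 17.5.1. This concerns outcome data only and changes no dose, stopping rule or treatment.

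The cost is about one sentence in Section 11.3.1.15, with a matching line in the AE collection period (Section 11.3.1.6) and in the consent text. Section 15.5 should say whether a remote contact counts as a visit for the end-of-trial definition. Contacts arise only if the event occurs. The downside is timing: outcome data for an affected cohort could arrive up to 64 − 22 = 42 days, about 6 weeks, after the nominal Visit 3.

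Separately, the 47-day Part B participation in the synopsis and Section 8.1.2 must be reconciled with a visit on Day 22 ± 2.
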